Pre-Analysis Plan for Study “Interventions to Improve HIV Antiretroviral Therapy Adherence in Beira, Mozambique”

September 10, 2018

This document outlines the pre-analysis plan for the project “Interventions to improve HIV antiretroviral therapy adherence in Beira, Mozambique.” The primary objective of the study is to test whether financial incentives and phone-call reminders improve medication adherence of patients on antiretroviral therapy (ART). Participants were randomly assigned at the individual level to one of four experimental groups:

1. Treatment Group 1 – receive **financial incentives** for refilling ART medications on time for six months
2. Treatment Group 2 – receive phone-call **reminders** before their ART medication refill date for six months
3. Treatment Group 3 – receive phone-call **reminders** before their ART medication refill date and **financial incentives** for on-time refills for six months
4. Control Group – no intervention.

Outcomes of Interest and Hypotheses

We list the outcome variables that we will analyze below. We have a single *primary outcome of interest*. Because we examine three treatments, we will apply a multiple hypothesis correction within the set of three treatment effect coefficients for this outcome variable.

We have *secondary outcomes of interest* as well. These include versions of the primary outcome of interest, specified differently, as well as highly related outcome measures. We will apply multiple hypothesis correction procedures to account for multiple outcome measures and multiple treatment groups. The secondary outcomes, as a group, will be considered separately from the primary outcome when the multiple hypothesis correction is applied.

Our multiple hypothesis correction procedure will be that of List, Shaikh, and Xu (2016), which incorporates information about the joint dependence structure of the test statistics, leading to gains in statistical power compared to more traditional approaches (such as Bonferroni (1935) and Holm (1979)). This approach is particularly attractive when working with outcome measures that are highly correlated.

Primary Outcome of Interest and Hypotheses

Medication possession ratio (MPR) at least 95%, 6-month window

This is a binary variable equal to 1 if MPR is greater than or equal to 95%, and 0 otherwise. MPR is the proportion of days that a participant is in possession of at least one ART dose. MPR is computed from pharmacy dispensing records. The measurement window is the 6-month follow up period. The measurement window will be truncated to the date that patients transfer clinics, opt out of future study participation, or die.

Hypotheses:

1. Hypothesis 1: Participants who receive the financial incentive intervention will have higher adherence to ART than those who receive no intervention.
2. Hypothesis 2: Participants who receive the phone-call reminder intervention will have higher adherence to ART than those who receive no intervention.
3. Hypothesis 3: Participants who receive both the financial incentive and the phone-call reminder interventions will have higher adherence to ART than those who receive only one intervention.

Secondary Outcomes of Interest

We will examine secondary outcomes that represent alternative ways to define medication adherence, to confirm that our results are robust to these alternate definitions. Hypotheses for these outcomes are analogous to those outlined above for the primary outcome.

We will examine the following alternate binary MPR variables as secondary outcomes. Definitions are analogous to the definition of the primary outcome of interest, but with modified adherence thresholds and/or measurement windows:

- Medication possession ratio (MPR) at least 95%, 3-month window
- Medication possession ratio (MPR) at least 80%, 6-month window
- Medication possession ratio (MPR) at least 80%, 3-month window

We will also examine the medication possession ratio (MPR) as a continuous variable, over two different measurement windows. This variable's definition, analogous to the definition of the primary outcome variable, is the proportion of days that a participant is in possession of at least one ART dose. It takes on values between 0 and 1 (inclusive). MPR is computed from pharmacy dispensing records. The measurement window will be truncated to the date that patients transfer clinics, opt out of future study participation, or die.

- Medication possession ratio (MPR), continuous variable, 6-month window
- Medication possession ratio (MPR), continuous variable, 3-month window

We also examine the following two additional variables that are relevant for ART adherence:

- Appointment attendance rate (AAR): AAR is the proportion of scheduled visits completed during the observation period. A visit is considered "completed" if the patient visits the clinic on the scheduled appointment date, or up to 7 days before that date. AAR is computed from clinic records. Measurement window truncated to last visit date for patients who transfer clinics, opt out of future study participation, or die.
- Lost to follow-up (LTFU): LTFU is a binary variable equal to 1 if a patient missed the last appointment and 90 or more days have elapsed since the patient's last scheduled appointment date, with no clinic record of contact since that date; and 0 otherwise. Patients who transfer clinics or opt out of future study participation are excluded from the LTFU denominator, but those who die are retained in the LTFU denominator.

Control variables

Regression specifications for analysis of treatment effects we will also include control variables to absorb residual variation and reduce standard errors of estimates. The control variables will be:

- Indicator: respondent is female
- Indicator: respondent is married
- Age (in years)
- Completed education (in years)
- One way travel time to clinic (in minutes)
- Knowledge about risk of missing ART doses (fraction of 4 questions answered correctly; takes on values of 0, .25, .5, .75, 1)¹
- Indicator: respondent is food insecure (ever skipped or reduced meal size in the last 12 months)
- Indicator variables for day of week of enrollment (one indicator for each of the following days of week: Monday, Tuesday, Wednesday, Thursday; Friday omitted)
- Indicator variable for enumerator (project staff member) administering enrollment and baseline survey (one indicator variable for each enumerator)

Because respondents are allowed to skip questions on the baseline survey, there may be missing values for some of these control variables. If any missing value exists for some variable “X”, we will create an indicator variable for variable X to flag missing status (1 if missing, 0 otherwise), replace the missing value of the variable X with zero, and include the variable X missing indicator variable in the set of control variables.

Data Adjustments to Be Conducted While Blind to Treatment Assignment

Observations will be excluded from the sample for analysis under the following circumstances.

1. MPR cannot be calculated
2. Three (3) or more control variables are missing values.

Balance Tests

We will test for balance of baseline characteristics across treatment groups. For each baseline variable, we will show p-values of F-tests of the joint hypothesis that means across all treatment conditions (Control and Groups 1, 2, and 3) are equal. We will also show the p-value of the single F-test of the joint hypothesis of equality of means across all treatment conditions, across all variables listed below.

- Indicator: respondent is female
- Indicator: respondent is married
- Age (in years)
- Completed education (in years)
- One way travel time to clinic (in minutes)
- Knowledge about risk of missing ART doses (fraction of 4 questions answered correctly; takes on values of 0, .25, .5, .75, 1)
- Indicator: respondent is food insecure (ever skipped or reduced meal size in the last 12 months)

¹ The component questions are all true or false responses to the following statements presented in the baseline survey (correct answers in parentheses): 1) Failure to adhere to ART doses does not increase the risk of transmitting (false), 2) Failure to adhere to ART can cause drug resistance and lead to treatment failure (true), 3) Failure to adhere to ART can increase the risk of AIDS (true), 4) Even if I stop medication, my immune system will function normally (false).

Regression Specifications and Hypothesis Tests

The primary regression specification is:

$$Y_i = \alpha + \beta_1 G_i^1 + \beta_2 G_i^2 + \beta_3 G_i^3 + \mathbf{X}_i + \epsilon_i.$$

The regression is run at the individual level. Y_i is the outcome of interest for individual i . G_i^1 , G_i^2 , and G_i^3 are treatment group indicators, that are equal to 1 if individual i is in the Treatment Group 1, 2, or 3, respectively, and 0 otherwise. \mathbf{X}_i is the vector of control variables described previously.

We will use a t-test $\beta_1 = 0$ to assess Hypothesis 1, t-test $\beta_2 = 0$ to assess Hypothesis 2, and t-test $\beta_3 = \beta_1$ and $\beta_3 = \beta_2$ to assess Hypothesis 3.

Subgroup Analysis

The regression for the primary outcome (MPR > 95%, 6-month window) will also be run in subgroups to assess heterogeneity of treatment effects. We will run regressions separately for subgroups defined below. For each of the treatment effects (β_1 , β_2 , and β_3), we will run a pair of regressions in corresponding subgroups, and test whether the coefficient is equal across the subgroups (e.g., between males and females).

- Male vs. Female
- Above or equal to median education vs. Below median education
- Food insecure vs. Not food insecure²
- Above or equal to median distance to the clinic vs. Below median distance to the clinic
- Above or equal to median knowledge about the risk of missing doses vs. Below median knowledge about the risk of missing doses

To correct for multiple hypothesis testing in this subgroup analysis, we will also use the method of List, Shaikh, and Xu (2016), accounting simultaneously for multiple subgroups and multiple treatments.

References

Bonferroni, C. E., *Il calcolo delle assicurazioni su gruppi di teste*. Tipografia del Senato, 1935.

Holm, S., "A Simple Sequentially Rejective Multiple Test Procedure," *Scandinavian Journal of Statistics*, 1979, pp. 65-70.

List, John, Azeem Shaikh, and Yang Xu, "Multiple Hypothesis Testing in Experimental Economics," NBER Working Paper 21875, January 2016.

² Food insecure is defined, as in the control variable, as having skipped or reduced the size of meals in the household in the last 12 months.

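### The primary-outcome multiplicity correction covers β1, β2 and β3, but the two contrasts that decide Hypothesis 3 lie outside it

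*SAP*

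**What the plan says.** Under Outcomes of Interest and Hypotheses, the SAP names one primary outcome and says that, because there are three treatments, "we will apply a multiple hypothesis correction within the set of three treatment effect coefficients for this outcome variable". The procedure is that of List, Shaikh and Xu.

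Under Primary Outcome of Interest and Hypotheses, three hypotheses are listed on an equal footing. The third reads: "Participants who receive both the financial incentive and the phone-call reminder interventions will have higher adherence to ART than those who receive only one intervention".

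Under Regression Specifications and Hypothesis Tests, each hypothesis is given its test. For the first two: "We will use a t-test $\beta_1 = 0$ to assess Hypothesis 1, t-test $\beta_2 = 0$ to assess Hypothesis 2". For the third: "t-test $\beta_3 = \beta_1$ and $\beta_3 = \beta_2$ to assess Hypothesis 3".

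Under Subgroup Analysis, the SAP shows what it means by treatment effects: "For each of the treatment effects (β_1 , β_2 , and β_3), we will run a pair of regressions in corresponding subgroups".

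For secondary outcomes, "Hypotheses for these outcomes are analogous to those outlined above for the primary outcome", and the correction there is to account for multiple outcomes and multiple treatment groups.

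**The concern.** The set that is corrected and the set that decides the hypotheses are different. The corrected set contains β3 = 0, which decides none of the three hypotheses. It omits β3 = β1 and β3 = β2, which are the only tests of Hypothesis 3.

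The SAP also does not say whether Hypothesis 3 needs both contrasts or only one. The phrase "will have higher adherence to ART than those who receive only one intervention" does not settle whether beating one single-intervention arm is enough.

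Whether a second intervention adds anything to the first is a separate claim from whether either works. As written, that claim could be reported from unadjusted p-values beside adjusted ones for Hypotheses 1 and 2, on the same primary outcome.

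**Working it through.** **Which tests are corrected (primary outcome)**

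| Test | Decides | In the corrected set? |
|---|---|---|
| β1 = 0 | Hypothesis 1 | yes |
| β2 = 0 | Hypothesis 2 | yes |
| β3 = 0 | none | yes |
| β3 = β1 | Hypothesis 3 | no |
| β3 = β2 | Hypothesis 3 | no |

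The SAP states no error rate, alpha or power, so there is no figure of its own to reproduce.

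**Assumptions.** Normal test statistics, two-sided 5%, four equal arms, Hypothesis 3 contrasts tested at |t| > 1.96. The List-Shaikh-Xu correction is approximated by a step-down max-|t| procedure.

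**Set-up.** Draw four independent arm means and form each contrast divided by √2. With equal arms, corr(β1, β2) = 0.5, corr(β3−β1, β3−β2) = 0.5, corr(β1, β3−β1) = −0.5 and corr(β2, β3−β1) = 0. The 95% points of max|t| are 2.35 for the three coefficients, about 2.46 for the four deciding tests and 2.52 for all five.

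**If either contrast suffices.** Under the global null:
- Within {β1, β2, β3} the error is 5.0%, as intended.
- For Hypothesis 3 alone it is 9.0%.
- Over the four deciding tests it is 11.6% single-step or 11.7% step-down. It stays between 11.2% and 12.1% over the unequal allocations tried (Control:1:2:3 of 1:2:2:2, 2:1:1:1, 3:1:1:1, 1.5:1:1:1 and 1:1:1:2).
- Counting favourable errors only, it is 6.3%, against 2.6% if all four tests were corrected together.

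**If both contrasts must favour the combination.** Errors on Hypotheses 1 and 2 are counted in both directions; step-down throughout:

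| True state | Plan as written | Four-test family |
|---|---|---|
| β1 = β2 = β3 = 0 | 4.1% | 2.8% |
| β1 = β3 large, β2 = 0 | 7.4% | 3.8% |
| β1 = β3 with 80% power at 1.96, β2 = 0 | 6.1% | 2.9% |

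The 7.4% can be checked by hand. Once β1 and β3 are rejected, step-down tests β2 = 0 at 5%. The contrast β3 − β2 is certain to be significant, so Hypothesis 3 is falsely claimed whenever β3 − β1 is significantly positive, which has probability 2.5%. These two tests use different pairs of arms (2 and Control; 3 and 1) and are independent, so the error is 1 − 0.95 × 0.975 = 7.4%. Counting only favourable errors on both, it is 1 − 0.975 × 0.975 = 4.9%.

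For Hypothesis 3 alone under this rule, a false favourable claim has probability 0.5% if β1 = β2 = β3, and 2.5% if β1 = β3 is large and β2 = 0.

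**The case against.** The strongest reply is that the SAP joins the two contrasts with the word and, so both must be significant. On that reading Hypothesis 3 is conservative by itself (0.5% to 2.5%) and the global-null error is about 4%, below 5%. The 12% figure belongs to the less natural reading. The 7.4% also mixes two-sided errors on β2 with one-sided errors on Hypothesis 3, although all the hypotheses are directional.

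Much of this stands. Requiring both contrasts is the natural reading, and it removes most of the excess. But the SAP does not state it as a decision rule, and it does not remove the excess in every case: counted one way throughout, the 4.9% is still about twice a 2.5% one-sided benchmark. The pattern that produces it, with incentives effective and reminders adding nothing, is a plausible one for this trial.

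It may also be said that a family of comparisons with Control suits the stated objective, and that the SAP never promises control over Hypotheses 1 to 3 together. That would be a fair design if Hypothesis 3 were labelled exploratory. It is instead listed beside the other two under the primary outcome.

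**Conclusion.** The point holds: the primary-outcome correction is wrong as written, because it leaves out both tests of one of the three primary hypotheses. The mismatch follows from the text and needs no assumption. Its size does: it depends on the assumed alpha, sidedness, allocation and normal approximation, and above all on the unstated decision rule. The excess is more than double the nominal 5% if either contrast counts. It is modest, and confined to states where some effects are real, if both must favour the combination.

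For secondary outcomes the wording is only unclear about whether the two contrasts are included. The subgroup analysis tests no Hypothesis 3 contrast and is not affected. This should be fixed before analysis.

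**What to change.** 1. Define the primary corrected family as β1 = 0, β2 = 0, β3 = β1 and β3 = β2, adding β3 = 0 only if it will be interpreted, and apply the List-Shaikh-Xu procedure to that family.
2. State that Hypothesis 3 is supported only if both contrasts are significant after correction and both favour the combination.
3. State alpha and sidedness.
4. State that the same contrasts belong to the secondary-outcome family. The subgroup section needs no change.

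**Cost in power** (equal arms):
- A Hypothesis 3 contrast with 80% power at 1.96 falls to about 64% (four tests) or 61% (five) in a single step. Four-test step-down gives 66% to 77%, depending on whether β1 and β2 are rejected first.
- With 80% power per contrast, both are significant 69% of the time uncorrected, and 48% (four tests) or 45% (five) in a single step. Four-test step-down gives 52% to 68%.
- A β1 or β2 test with 80% power at 2.35 falls to about 77% or 75%.

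A somewhat cheaper variant enters Hypothesis 3 as one hypothesis, using the larger of its two p-values, so that the family has three members. A Bonferroni bound for three hypotheses (|t| of 2.39) then gives about 51% for both contrasts, against 48% above. Either version is sound if written down in advance.

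### For patients who transfer, opt out or die, the appointment attendance rate stops at an undefined last visit date, whereas MPR stops at the event; read as last attended visit, the rule discards the misses in between.

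*SAP*

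**What the plan says.** Under Secondary Outcomes of Interest, the SAP defines the outcome thus: "AAR is the proportion of scheduled visits completed during the observation period". A visit counts as completed "if the patient visits the clinic on the scheduled appointment date, or up to 7 days before that date". For patients who leave the study or die, the rule is: "Measurement window truncated to last visit date for patients who transfer clinics, opt out of future study participation, or die".

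For MPR, both in the primary outcome and in the continuous secondary versions, the rule for the same three events is different: "The measurement window will be truncated to the date that patients transfer clinics, opt out of future study participation, or die".

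The bullet on loss to follow-up (LTFU), directly after AAR, uses explicit wording when it means a scheduled date: "90 or more days have elapsed since the patient's last scheduled appointment date". It also states: "Patients who transfer clinics or opt out of future study participation are excluded from the LTFU denominator". Deaths stay in that denominator.

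Under Data Adjustments to Be Conducted While Blind to Treatment Assignment, the only exclusion tied to an outcome is "MPR cannot be calculated". The other exclusion concerns missing control variables.

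**The concern.** The AAR cut-off is undefined, differs from the MPR cut-off for the same patients and events, and comes without a reason for the difference. Two analysts following the SAP could compute different AARs for one patient.

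On the attended-visit reading there is a substantive fault: the window ends on an attendance, so its length depends on the outcome being measured. The appointments a patient missed before the event are exactly the ones removed, and AAR for that patient is generally too high.

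AAR is there to support the primary result, is regressed on the same three treatment indicators, and enters the secondary multiplicity correction. For transfers and opt-outs LTFU does not pick up the lost misses, because those patients leave its denominator; only the MPR outcomes cover the gap. The interventions aim at timely attendance for refills, so the number of misses before the event, the event rates, or the way events are discovered may differ by arm. The error then need not cancel.

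**Working it through.** **Inputs.** From the SAP: the AAR definition, the 7-day completion rule and the two truncation rules. The SAP gives no visit interval, event rate or expected AAR, so there is no figure of its own to reproduce. All visit counts and shares below are assumptions.

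**Which reading.** Within the AAR bullet, the noun *visit* is used for a scheduled slot and the verb for actual attendance, so the bullet does not settle the matter. Two things favour attendance: a visit date in clinic records is usually the date the patient came, and the adjacent LTFU bullet says scheduled when it means scheduled.

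**Per patient, attended-visit reading.** Let *a* be the appointments kept and *m* those missed after the last attendance and before the event, with no earlier misses.

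- Cut at last attended visit: AAR = a/a
- Cut at event date (the MPR rule): AAR = a/(a + m)

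| Kept, then missed | Cut at last attended visit | Cut at event date | Difference |
|---|---|---|---|
| 5, 1 | 5/5 = 100% | 5/6 = 83.3% | +16.7 points |
| 3, 2 | 3/3 = 100% | 3/5 = 60% | +40 points |
| 1, 4 | 1/1 = 100% | 1/5 = 20% | +80 points |
| 0, n | 0/0, undefined | 0/n = 0% | not computable |

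The last row has no handling rule, since the exclusions mention only an MPR that cannot be calculated.

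**A case in the other direction.** Suppose the first appointment is missed and the second is kept a few days early. The window closes on the day of attendance, before the second appointment's own date. If that appointment is then taken to lie outside the window, AAR = 0/1 = 0% instead of 1/2 = 50%, an understatement of 50 points.

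**Scheduled-visit reading.** If the window ends at the last scheduled visit before the event, all *m* misses remain and AAR = a/(a + m), the same as under the event-date cut.

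**Between arms.** With the same overstatement per affected patient in both arms, bias = (difference in affected share) × (overstatement per affected patient):

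- equal shares: 0 × any value = 0
- shares differing by 2 percentage points (say 5% against 3%): 0.02 × 16.7 = 0.3 points, up to 0.02 × 80 = 1.6 points
- shares differing by 5 percentage points: 0.05 × 16.7 = 0.8 points, up to 0.05 × 80 = 4.0 points

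Equal shares give zero only if the overstatement per patient is also equal. If one arm has more misses before the event, bias remains even with equal shares.

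**The case against.** The strongest reply is that the attended-visit reading is not forced. In the AAR bullet a visit is something that may or may not be completed, which describes a scheduled slot, and the LTFU bullet speaks of appointments and never uses the noun *visit*. The contrast between the two bullets may therefore be one of vocabulary. On the scheduled reading the loss of misses disappears, and the different wording from MPR is harmless: MPR counts days and needs a calendar cut, while AAR counts visits and may reasonably end at one.

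For transfers, stopping at the last attended visit can also be defended, because appointments after care has in practice moved are not true misses. Finally, the between-arm sizes are assumed throughout, and the 4.0-point figure applies an extreme patient pattern to everyone affected.

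Much of this stands. The term is open to both readings, the ranges only illustrate, and the reach is narrow. It does not remove the point. Under one reading the term needs a definition; under the other, more usual one, the stated rule discards misses. The argument about transfers is weaker for opt-outs and deaths, and the MPR window already accepts the same imprecision for late-recorded transfers.

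**Conclusion.** The concern holds, conditionally on the reading. The SAP sets two cut-offs for the same events, leaves one undefined, and on its more natural reading lets attendance decide which missed appointments count.

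The overstatement for an affected patient is 16.7 to 80 points for the end cases in the table. The effect on an arm comparison is unknown: zero if affected shares and overstatement are equal, and 0.3 to 4.0 points for assumed differences in share of 2 to 5 percentage points.

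Only patients who transfer, opt out or die after at least one such miss are overstated. Patients who simply stop attending keep all their misses. AAR is weakened as a supporting outcome, not disabled. This should be corrected, but it does not threaten the main conclusion.

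**What to change.** Truncate AAR at the date of transfer, opt-out or death, as for MPR. Put in the denominator every appointment scheduled up to that date, with missed ones scored as not completed. State that an appointment kept within the permitted early window counts in both numerator and denominator, even if its own date falls after the cut.

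If the last-visit rule is kept, define the term, say why it differs from the MPR rule, and state how 0/0 is handled.

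The cost is one or two sentences; the event dates are already needed for MPR. The one drawback is that appointments missed after a patient has in practice moved clinic, but before the transfer is recorded, will count as missed. The MPR window already treats those days in the same way.

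### Does leaving adherence before enrolment out of the control variables weaken the analysis?

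*SAP*

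**What the plan says.** The SAP's *Control variables* section gives one reason for adjustment: the regressions use "control variables to absorb residual variation and reduce standard errors of estimates". It then lists sex, marital status, age, education, travel time to the clinic, a knowledge score, food insecurity, weekday of enrolment and enumerator. The item nearest to adherence is "Knowledge about risk of missing ART doses (fraction of 4 questions answered correctly; takes on values of 0, .25, .5, .75, 1"), which measures knowledge and not behaviour. Under *Regression Specifications and Hypothesis Tests*, the term X in the model "is the vector of control variables described previously", so the same list enters every treatment-effect regression.

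On the outcome, *Primary Outcome of Interest and Hypotheses* says that "MPR is computed from pharmacy dispensing records" and that "The measurement window is the 6-month follow up period". No window before enrolment is defined. The population is described only through the objective, which is to "improve medication adherence of patients on antiretroviral therapy (ART"). Time on treatment at enrolment is not given.

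The section headed "Data Adjustments to Be Conducted While Blind to Treatment Assignment" adds a rule that touches any extra covariate: an observation is dropped if "Three (3) or more control variables are missing values".

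**The concern.** If the only purpose of the controls is to reduce standard errors, the natural candidate is the outcome's own value before treatment. The plan leaves it out, although the participants are already on ART and the outcome comes from a record system that may reach back before enrolment. Demographics and a knowledge score may explain little of the variation in refill behaviour.

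At stake would be precision for the six MPR outcomes: the primary, three other binary versions and two continuous versions. Every contrast would be affected alike: the incentive effect, the reminder effect, and the two comparisons of the combined arm with each single arm under Hypothesis 3. Wider intervals than necessary could cost a true effect its significance.

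**Working it through.** The SAP gives no R², sample size, significance level or power, so there is no figure of its own to reproduce. The check has four steps.

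**1. Is anything biased?** Allocation is random at the individual level, so the group indicators are independent in expectation of prior adherence, and omitting it leaves the treatment coefficients unbiased. A simulation with assumed inputs (600 participants, four equal arms, binary outcome, linear model) agrees. With a baseline variable correlated 0.39 with the outcome, the mean estimate was 0.0999 without it and 0.1001 with it. The standard errors without the covariate are larger but correct, so the false-positive rate is not affected.

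**2. How large could the precision loss be?** Let R² be the share of the remaining outcome variance that prior MPR explains beyond the listed controls, and c the share of participants with a usable history. Then the reduction in the standard error is 1 − √(1 − c·R²). For example, with c = 1 and R² = 0.10: 1 − √0.90 = 5.1%. All inputs are assumed:

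| Share with history | R² = 0.02 | 0.05 | 0.10 | 0.20 |
|---|---|---|---|---|
| All | 1.0% | 2.5% | 5.1% | 10.6% |
| Half | 0.5% | 1.3% | 2.5% | 5.1% |
| A quarter | 0.3% | 0.6% | 1.3% | 2.5% |
| A tenth | 0.1% | 0.3% | 0.5% | 1.0% |
| None | 0% | 0% | 0% | 0% |

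The upper end is itself a choice. A partial correlation of 0.6 (R² = 0.36) gives 1 − √0.64 = 20.0% with full history, and 1 − √(1 − 0.25 × 0.36) = 4.6% with a quarter. A comparison with an assumed 80% power (two-sided 0.05, also assumed) would move to 80.4% at a partial correlation of 0.1 and to 93.8% at 0.6. The SAP does not say where in this range the trial lies.

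**3. Does the SAP show that the covariate is available?** No. The dispensing records are mentioned only for the follow-up window. Both c and R² depend on time on ART and on access to earlier records, which this document does not give and which a protocol may cover.

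**4. Would adding it be simple?** Not clearly.
- It needs a further data extraction whose effort cannot be judged from the SAP.
- Recent starters are awkward. Someone first dispensed a 30-day supply 20 days before enrolment (illustrative) has 20/20 = 1 if counting starts at first dispensing. That is the same value as six months of full possession, but it says nothing about adherence. A minimum history length would have to be chosen.
- A missing history would count towards the three-missing exclusion rule, so two skipped survey items would then remove a person. If each of the seven survey controls is missing independently with probability q (assumed), the chance of exclusion for someone without history goes from P(at least 3 of 7) to P(at least 2 of 7): 0.03% to 0.8% at q = 0.02, 0.4% to 4.4% at q = 0.05, and 2.6% to 15.0% at q = 0.10. An exemption would have to be written. The addition creates this problem; the present plan does not have it.

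**The case for a change.** The best case for the concern is that it measures the list against the plan's own aim. Precision is the stated purpose, most outcomes are possession measures, the data come from records and not from recall, and the list still holds no earlier value of the outcome. The advice could also be made conditional: use prior MPR if the records are there, otherwise leave the model alone.

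Three parts of this stand. The list does contain no prior adherence measure. Where good history exists, adjusting for it would reduce the standard error. And the relation used for the size is sound: in the simulation above, the ratio of standard errors was 0.921 at a correlation of 0.39, close to √(1 − 0.39²) = 0.921.

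What does not stand is the step from possibly useful to badly fixed. That step needs a baseline value which the trial is shown to collect, or can obtain at known small cost, and the SAP shows neither. It also has to be weighed against changing a dated, pre-specified primary model after participants have been assigned. The blinding named in the section heading covers treatment assignment and does not mention outcomes, so a covariate chosen now would need its own safeguard.

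**Conclusion.** The concern does not hold. The control set is closed, applied consistently and valid under individual randomisation; nothing in the SAP contradicts it. Omitting prior MPR causes no bias and no excess false positives. The possible cost is precision alone, between 0% and 10.6% of the standard error for an assumed partial R² of up to 0.20, and up to 20.0% at 0.36. Both ends rest on assumptions about records and treatment history that the document does not settle. Another statistician might have chosen a different covariate, but that is a preference between valid models.
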